#### 10.5 Physical Examination and Visual Examination of Oral Cavity

A full physical examination will be performed at Screening Visit 1 only. A data listing of the physical examination results will be performed.

A visual examination of the oral cavity will be assessed at Screening, Baseline, and Week 12. A visual examination is to be done any time a participant spontaneously reports an oral adverse event (aside from AEs known to be sensory-only, such as numbness, tingling or bitter taste) to confirm presence or absence of any signs of irritation or other visible abnormalities. A data listing of the visual examination results performed at each scheduled visit and at the time of an adverse event will be presented.

### **10.6 Electrocardiogram (ECG)**

A 12-lead ECG will be performed only at the Screening Visit. The standard ECG parameters including rhythm, heart rate, and intervals for PR, QRS, QT and QTcF (Fridericia's) correction for heart rate will be recorded. A data listing of ECG results will be provided.

### **10.7 Assessment of Sedation Morning Treatment-Related Sedation Score (MTRSS)**

The MTRSS is designed to assess the participant's one-week recall of morning sedation as assessed at clinic visits. The MTRSS will be assessed at Baseline (Visit 2) and at Weeks 4, 8, and 12 (Visits 4, 5, and 6). The participant will complete the following questions:

(A) On most mornings during the past week, I have awakened feeling:

0. Alert with no grogginess
1. Mildly groggy
2. Moderately groggy
3. Very groggy

(B) If you reported any grogginess in the last week (responses 1-3), the grogginess lasted:

1. A few minutes
2. A short time (less than one hour)
3. A long time (more than one hour)

Note: if "Alert with no grogginess" is selected in Part A, Part B is not completed, and the score for part B is 0

Results will be summarized with counts and percentages at each visit.

### **10.8 Assessment of Changes in Sexual Function: Changes in Sexual Functioning Questionnaire Short-Form (CSFQ-14)**

The CSFQ-14 ([Keller et al. 2006](#)) is a validated scale with internal reliability designed to allow a participant to self-evaluate his or her sexual behaviors or problems in several areas. The CSFQ-14 will be administered at Baseline (Visit 2) and Week 12/ET (Visit 6). It yields a total score, three subscales corresponding to phases of the sexual response cycle (i.e. desire, arousal, orgasm), and five subscales corresponding to important dimensions of sexual functioning. It is considered a useful scale for assessing sexual side effects of medications. For all items, higher scores reflect higher sexual functioning. For

12 of the 14 items, higher sexual functioning corresponds to greater frequency or enjoyment/pleasure (e.g. 1=never to 5 = every day). For two items (item 10, assessing loss of interest after arousal for women and priapism for men, and item 14, assessing painful orgasm), higher sexual functioning corresponds to lower frequency (e.g. 1=every day to 5=never). Items 10 and 14 are included in the total score but not in any scale score.

Descriptive summaries (mean, SD, median, minimum, and maximum) of actual values and changes from baseline at each assessment time point will be reported.

## 11. MEDICATIONS

### 11.1 Concomitant Medication

All medications will be coded using the World Health Organization Drug Dictionary (WHO-DD) Version September 2016. Prior and concomitant medications will be summarized by treatment group and by the number and percentage of participants taking each medication, classified by using WHO-DD Anatomical Therapeutic Chemical Level 3 and preferred term.

Prior medications are defined as medications or therapies initiated prior to the start of the study drug and terminating prior to the start of study drug. Hence, these medications or therapies will have end dates prior to the first dose date of study drug. Concomitant medications are defined as any medications other than the study drug that a participant receives concurrently with the study drug. These medications will have end dates on or after the first dose date of the study drug until ten days after last dose date.

Prior and Concomitant medications will be summarized. All medications will be presented in a listing.

Participants' Lifetime Prior Psychiatric Medications (i.e., discontinued  $\geq 60$  days prior to the Screening visit) will also be summarized by treatment group and by the number and percentage of participants taking each medication, classified by using WHO-DD Anatomical Therapeutic Chemical Level 3 and preferred term.

Please refer to [Section 7.3](#) for the conventions used to impute partial start dates and end dates of concomitant medications.

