#### 7.3.1 Adverse Event and Prior/Concomitant Medication handling conventions

To handle missing or partial AE and prior/concomitant medication dates, the following rules will be applied.

For partial start dates:

1. If the year is unknown, then do not impute the date but assign a missing value.
2. If the month is unknown, then:

- a. If the year matches the year of the first dose date, then impute the month and day of the first dose date.
  - b. Otherwise, assign “January.”
3. If the day is unknown, then:
- a. If the month and year match the month and year of the first dose date, then impute the day of the first dose date.
  - b. Otherwise, assign “01.”

For partial end dates:

1. If the year is unknown, then do not impute the date but assign a missing value.
2. If the month is unknown, then assign “December.”
3. If the day is unknown, then assign the last day of the month.

Adverse events are categorized as either pre-treatment adverse events or treatment-emergent adverse events based on the response to the CRF question “Did the AE start prior to the first dose?”

After implementing the rules above, to determine whether medications with missing start or stop dates are prior or concomitant medications, the following strategy will be used:

1. If the start date and stop date are both missing, then the most conservative approach is taken and the medication is considered to be a concomitant medication.
2. If the start date is missing but the stop date is not missing and is after the day of first study dose administration, then the most conservative approach is taken and the medication is considered to be concomitant.
3. If the start date is missing but the stop date is not missing and is on or before the day of first study dose and after the date of signed informed consent, then the medication is considered to be a prior medication.
4. If the start date is not missing but the stop date is missing, then the most conservative approach is taken and medication is considered to be concomitant.

The missing severity of an AE will be imputed to “severe”; the missing relationship to study drug of an AE will be imputed to “related”.

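### SAP 11.1's ten-day limit on end dates conflicts with its own concurrent-use definition and, with uncapped end-date imputation in SAP 7.3.1, leaves some on-treatment medicines in neither the prior nor the concomitant table

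*SAP*

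**What the plan says.** SAP 11.1 gives a definition by use: "Concomitant medications are defined as any medications other than the study drug that a participant receives concurrently with the study drug". It follows this with a condition on the end date: "These medications will have end dates on or after the first dose date of the study drug until ten days after last dose date". For prior medicines it says: "Hence, these medications or therapies will have end dates prior to the first dose date of study drug".

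SAP 7.3.1 completes partial end dates. One rule reads: "If the day is unknown, then assign the last day of the month". A further rule sets the month: "If the month is unknown, then assign “December"; together with the day rule, that gives 31 December. Neither imputation is capped at last dose, last visit or last contact. If the year is unknown, the date is left missing.

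After imputation, SAP 7.3.1 adds four rules. Their stated scope is "to determine whether medications with missing start or stop dates are prior or concomitant medications, the following strategy will be used":
- Rule 1: both dates missing, concomitant.
- Rule 2: "If the start date is missing but the stop date is not missing and is after the day of first study dose administration", concomitant. There is no ten-day limit.
- Rule 3: start missing, stop on or before the first-dose day and after consent, prior.
- Rule 4: start present, stop missing, concomitant.

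SAP 11.1 also plans by-arm summaries of prior and concomitant medicines and a listing of all medicines.

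**The concern.** Concurrent use means that the period of use overlaps the period of treatment. An upper limit on the end date does not test for that, because a medicine taken every day of treatment and stopped two weeks later is plainly concurrent. The SAP's other ten-day window, for treatment-emergent adverse events in SAP 10.1, applies to the onset of new events. In SAP 11.1 it has been attached to the end date.

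The imputation in SAP 7.3.1 pushes further records past that limit. Some records with partial information could then leave both tables, while the same record with no end date would stay in. Two programmers, one following the definition and the other the end-date sentence, would produce different tables.

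The tables matter modestly. Protocol 8.5 describes an evaluation of monotherapy. Protocol 8.5.1 permits short-term antihistamine hypnotics and stable melatonin, and warns that decongestants could confound the comparison. SAP 11.1 is the planned by-arm summary of such permitted medicines.

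**Working it through.** The plan states no figure on this point, so there is none to reproduce. The check applies the rules literally.

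**Inputs.** Prior: end < first dose. Concomitant: first dose ≤ end ≤ last dose + 10 days (SAP 11.1). Day unknown becomes month-end; month unknown becomes 31 December (SAP 7.3.1). Treatment lasts 84 days (Protocol 10.5, Visit 6), with 56 and 28 days run for early terminators. Assumptions not in the documents: start date known, last-dose dates spread evenly over a 365-day year, true end date uniform over the treatment days.

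**Worked case.** First dose 16 January 2018, last dose 9 April 2018 (84 days); the window closes on 19 April. The medicine was started before or during treatment and truly ended on 5 April.

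| How it is recorded | End date used | Class |
|---|---|---|
| Full dates | 5 April | concomitant |
| Start known, end *Apr 2018* | 30 April | neither |
| Start known, end *2018* | 31 December | neither |
| Start known, end blank | missing | concomitant (rule 4) |
| Start missing, end *Apr 2018* | 30 April | concomitant (rule 2) |

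A complete end date of 20 April or later, with a known start, is also in neither class.

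**Day unknown.** A record is lost only if its true end is in the calendar month of last dose and month-end is more than ten days after last dose. In a month of L days this needs last dose on day d ≤ L − 11, and then d treatment days are at risk.
- Last-dose dates affected: 7 × 20 + 4 × 19 + 17 = 233 of 365 (64%).
- Treatment days at risk: 7 × 210 + 4 × 190 + 153 = 2383, or 2383/365 = 6.53 per participant.
- Share of on-treatment end dates: 6.53/84 = 7.8%; 6.53/56 = 11.7%; 6.53/28 = 23.3%.

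**Month unknown.** A record is lost if its true end is in the calendar year of last dose and last dose is on or before 20 December (day 354). For last dose on day y, min(y, treatment length) treatment days are at risk.
- 84 days: (83 × 84/2 + 271 × 84)/(365 × 84) = 26,250/30,660 = 85.6%.
- 56 days: (55 × 56/2 + 299 × 56)/(365 × 56) = 18,284/20,440 = 89.5%.
- 28 days: (27 × 28/2 + 327 × 28)/(365 × 28) = 9,534/10,220 = 93.3%.
- Last-dose dates affected: 354 of 365 (97%).

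**First-dose day.** A medicine with a missing start that ends on the day of first dose (and after consent) is prior under rule 3 of SAP 7.3.1, but has an end date inside the concomitant window of SAP 11.1.

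**The case against.** The strongest reply is that SAP 11.1 defines concomitant medication by concurrent use, and the end-date sentence only describes what follows from that. On this reading a medicine taken on treatment counts whatever its imputed end date, and rules 1, 2 and 4 of SAP 7.3.1 lean the same way. This stands in part. A reader might infer that the SAP classifies by end date alone and so requires the loss; it does not. It contains two sentences that give different answers, and nothing says which governs.

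A reader might also take 64% and 97% as the share of partial dates lost. Those are shares of last-dose dates, and apply only to a medicine whose end is already known to be in the month or year of last dose. Over 84 days most on-treatment ends are in earlier months, whose month-end is inside the window, so the day-unknown share is about 8%. Year-only ends should also be unusual for medicines stopped on study, because concomitant medication is updated at the Week 2 call and at Weeks 4, 8 and 12 (Protocol 10.3 to 10.5).

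The gap for complete dates is narrow too. Scheduled collection ends at Visit 6 or early termination, and a medicine still in use then has no stop date and is kept under rule 4. The gap would arise mainly at a late early-termination visit, which Protocol 10.5.1 does encourage even after a lapse in dosing.

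Finally, a reader might infer that records disappear, that excluded medicines have no other by-arm display, or that the comparison of background treatment would be wrong. All medicines are listed, and SAP 8.2 summarizes deviations by type and arm, where prohibited medicines would be expected. The rule is the same in both arms, and nothing in the documents shows a differential effect.

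**Conclusion.** The point holds as a minor error in a stated rule. The end-date sentence in SAP 11.1 contradicts that section's own definition and sits badly with rules 2 and 4 of SAP 7.3.1. Those rules do not rescue the affected records, because they apply only to dates still missing after imputation.

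The percentages above are shares of records with a known start and a partial end date that were taken on treatment, not of all medicines. They rest on even spread of last-dose dates and uniform end dates. The documents give no frequency of partial dates, so the number of records lost cannot be stated. The day-unknown share is about three times larger at 28 days of treatment than at 84, so early terminators are the more exposed group.

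The consequence is limited to possible undercounting in descriptive by-arm medication tables. No efficacy inference uses this classification.

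**What to change.** Replace the end-date sentence in SAP 11.1 with one overlap rule:
- Concomitant: start on or before last dose (or missing), and end on or after first dose (or ongoing or missing). No upper limit on the end date.
- Prior: end before first dose.

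If the ten-day post-dose window is wanted, apply it to the start date and say so, since it would then admit medicines begun after study drug had stopped. Have SAP 7.3.1 refer to this rule, and use one first-dose-day convention in SAP 11.1 and in rules 2 and 3 of SAP 7.3.1.

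Capping imputed end dates is optional, because the overlap rule already classifies these records. Under it the on-treatment share in neither table is zero by construction, including complete end dates beyond the present window.

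Cost: a couple of SAP sentences and one derivation line, with no new data.

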### 11.2 Exposure and Compliance

The treatment duration will be calculated as (number of days=last dose date - first dose date+1) and summarized. Participants that are lost to follow up or have a missing last dose date will be assigned a last dose date of the day before the last attended clinic visit for analysis purposes.

All pill count shortage (negative pill count) of greater than 4 doses (8 tablets) per 4-week assessment period and/or any between-visit compliance <70% will be considered protocol deviations, and the reason for the pill count discrepancy will be discussed with the participant and documented in the CRF to ensure that any cases of potential abuse or misuse are identified. Participants with more than one significant incidence of negative pill count discrepancy during the double-blind phase of the study will be closely monitored by the investigator.

Exposure will be measured using the last date of treatment and first date of treatment. Total exposure will be defined as the last date of treatment minus the first date of treatment plus one. The number of participants with total exposure by visit weeks ( $\leq 4$  weeks (study day 0 to 28), 4 to  $\leq 8$  (study day 29 to 56), 8 to  $\leq 12$  (study day 57 to 84) and  $> 12$  weeks (study day  $\geq 85$ )) will be presented. Additionally, exposure days, defined as the total number of tablets taken divided by 2 (and rounded up to the nearest whole number), will be summarized.

Compliance will similarly be summarized across all study visits for each treatment arm. Study drug compliance as a percentage will be defined as the number of pills taken by the participant divided by the total number of pills that the participant was assigned to take multiplied by 100.

For calculating the compliance and exposure days, the following convention will be applied: for periods where drug is issued, but the participant does not return any bottles or tablets, or the participant misses the visit entirely, that period will not contribute to the compliance or exposure calculation unless the bottles are returned at a later visit.

Compliance will be summarized with descriptive statistics by treatment arm. The number and percentages of participants within certain categories of compliance e.g. < 50%, 50% to < 70%, 70% to <= 100%, greater than 100% will be presented. Compliance between 70% to 114% will not be considered a protocol deviation. Tablet counts, calculation of compliance overall and by visit, and participant-reported reasons for all tablet discrepancies at all visits will be presented in a listing.

In addition, participants with significant over-usage or otherwise unaccounted-for missing tablets resulting in >114% compliance for any visit (e.g., failure to return >8 tablets per 4 week interval) will be summarized by visit and overall. These listings will include both the participant-reported reason for the discrepancy plus the investigator's assessment of potential abuse, misuse or diversion. Tables will be created for higher level abuse-related MedDRA terms. Clinically significant drug accountability discrepancies associated with missing medication, loss of drug, or cases in which the PI confirms concern over drug abuse, misuse or diversion, will be examined and discussed in the CSR.

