9.2. Dosing Instructions

Patients will be instructed to take **two** tablets of their assigned study drug (TNX-102 SL 2.8 mg tablets or placebo tablets) sublingually, placed simultaneously **under the tongue**, each evening at bedtime starting at bedtime on evening of Day 0 (Day of Visit 2) and continuing without interruption for 12 weeks. The study drug should be taken at bedtime after teeth brushing and other oral care has been completed. The mouth/sublingual area should be moist at the time of dosing, so the patient should drink a few sips of water prior to dosing, especially if prone to dry mouth. Patients will be instructed to place the two SL tablets under their tongue and keep them there until they have dissolved. They should not swallow, crush or chew the tablets. Patients should not eat or drink (or chew gum) for at least 15 minutes after dosing, and preferably not until morning. Patients will be reminded that only 2 (two) tablets are allowed per day. Note: In the event that the patient misses a dose, instruct the patient to continue dosing with two (2) tablets the next evening; i.e., they should not take more to make up for the missed dose.

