10.3. Visit 3 (Telephone Visit: Day 14)

Visit 3 will be done as a telephone call to the patient and should be conducted after 2 weeks of treatment, on Day 14 \pm 3 days.

The following steps should be completed:

- Assess changes in concomitant medications
- Assess study drug compliance based on patient verbal report
- Assess occurrence of adverse events, including any oral adverse events and whether an unscheduled visit is indicated for an examination of the oral cavity
- Review patient instructions regarding drug dosing.
- Administer the ‘Since Last Visit’ C-SSRS

After all of the items have been reviewed with the patient, the patient should be given an appointment to return to the clinic for Visit 4, and be re-instructed, as necessary, on dosing instructions, and reminded to bring study medication back to the clinic at their next visit.

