10.5.1. Early Termination (ET)

In accordance with the Declaration of Helsinki, patients have the right to withdraw from the study at any time for any reason, and they will be advised of this right. The investigator and Tonix also have the right to remove patients from the study. Specific reasons for removal of a patient from the study could include, but are not limited to:

- An adverse event (AE)
- An illness that, in the judgment of the investigator or Tonix, might invalidate the study results or place the patient at risk
- The request of the patient, investigator, or Tonix, whether for administrative or other reasons
- Pregnancy

This study will attempt to obtain as complete information as possible on all participating patients. An effort must be made to contact the medical monitor prior to any patient's early termination. Each reason for early termination will be adjudicated. Patients who wish to terminate their participation in the study should be instructed to come to the clinic for an Early Termination Visit. The purpose of the Early Termination visit is to obtain critical information about the patient's participation, and should be scheduled preferably before there has been a substantial lapse in study medication usage. However, even if there has been a medication lapse, the patient should be encouraged to return to the clinic for this visit, and should be instructed to return all study medication. NOTE: These visit procedures are not intended for patients who fail to qualify for randomization or for any other reason withdraw from the study prior to receipt of a dose of double-blind study drug.

If the patient withdraws prior to the week 2 (visit 3) visit window (before day 11), the following assessments and procedures are to be completed at this visit in the following general order:

- Document reason for early termination
- Collect study drug and assess compliance
- Assess occurrence of adverse events
- Update concomitant medications
- Obtain vital signs and weight
- Conduct urine pregnancy test (for women of child-bearing potential). Serum pregnancy test may be done at Investigator's discretion.
- Draw samples for clinical laboratory tests for:
 - Chemistry and hematology
- Perform visual examination of oral cavity
- Have the patient complete the following outcome scales (in order):
 - MTRSS (assessment of sedation)
 - CSFQ-14
 - BDI-II (needs to be completed prior to the C-SSRS and reviewed by the C-SSRS rater at outset of C-SSRS interview)

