### **3. OVERALL STUDY DESIGN AND PLAN**

This is a Phase 3, 12-week, randomized, multicenter, double-blind, placebo-controlled, fixed dose study that will investigate the efficacy and safety of TNX-102 SL 5.6 mg taken daily at bedtime for the management of military-related PTSD. This study is to be conducted at approximately 45 investigational sites in the United States.

The total duration of this study over 6 visits will be approximately 13-17 weeks, with 12 weeks of treatment duration and a variable length of screening. This study will consist of a Screening visit (Visit 1, Days -35 to -7), Randomization visit (Visit 2, Day 0), telephone visit (Visit 3, Week 2) and three monthly in-clinic visits (Visits 4, 5 and 6 at Weeks 4, 8, and 12).

Eligible participants who provide written informed consent to participate will have study assessments performed at Screening, including counseling regarding any required washout and instructions to refrain from use of excluded medications throughout the study.

The length of the pre-randomization screening period is variable (7 to 35 days) in order to accomplish wash-out of previous medications, where appropriate, and allow for return of clinical laboratory results necessary to confirm eligibility. At Visit 2, participants will return to the site for additional baseline assessments and randomization (Day 0), when, if they meet all study randomization criteria, they will be randomly assigned in a 1:1 ratio to receive placebo or TNX-102 SL 5.6 mg. A dynamic randomization procedure will be employed at Visit 2 to minimize trial-wide imbalances between the treatment groups for site, sex, current tobacco/nicotine use (yes/no) and presence (yes/no) of current Major Depressive Episode (MDE) based on the Mini International Neuropsychiatric Interview, Version 7.0.2 (MINI 7.0.2) conducted at Visit 1.

Participants will take the study drug sublingually daily at bedtime, starting on the day that they are randomized and continuing for 12 weeks. Participants will return to the study center for safety and efficacy assessments at Weeks 4, 8, and 12 (or early termination [ET]).

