### **10.1 Adverse Events**

All AEs, treatment-emergent adverse events (TEAEs), and SAEs will be coded using MedDRA, version 19.0.

TEAEs are defined as either new onset AEs with an onset at the time of or following the start of treatment through ten days after the last dose of study medication, or a recurrence of an AE (or medical history) present prior to randomization but increasing in severity, frequency or relationship at the time of or following the start of treatment

An AE summary table will be presented for the following:

- TEAEs by severity
- TEAEs leading to study drug discontinuation
- TEAEs by relationship
- SAEs

Summaries of incidence rates (frequencies and percentages) of individual AEs by MedDRA SOC and preferred term will be prepared. Such summaries will be displayed for all TEAEs, TEAEs by maximum severity, and TEAEs by strongest relationship to study drug.

Each participant will be counted only once within each summation level (SOC; preferred term). If a participant experiences more than one TEAE within each summation level only, the TEAE with the strongest relationship or the maximum severity, as appropriate, will be included in the summaries of relationship and severity.

Adverse events of special interest pertaining to abuse potential (as defined in the January 2017 Assessment of Abuse Potential for Drugs – Guidance for Industry) will be analyzed separately by treatment group, SOC and preferred term, and displayed in tabular format.

In the AE data listings, all AEs will be displayed. AEs that are treatment-emergent will be flagged.

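### The last-dose imputation in SAP 11.2 can precede the first dose: a participant lost after the Week 2 call, with no later visit, gets 0 days of treatment

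*SAP*

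**What the plan says.** SAP 11.2 defines duration and the imputation together: "The treatment duration will be calculated as (number of days=last dose date - first dose date+1) and summarized". The imputation covers two groups, those lost to follow-up and those for whom no date of last dose is recorded, who "will be assigned a last dose date of the day before the last attended clinic visit for analysis purposes". It sets no lower limit at the first dose date and makes no exception for telephone contact.

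Protocol 9.2 starts dosing at bedtime on the day of Visit 2. On the next scheduled contact, Protocol 10.3 states: "Visit 3 will be done as a telephone call to the patient". That call is due on Day 14 ± 3 and asks for a verbal report of compliance and for adverse events, including oral ones. SAP 3 likewise separates the Week 2 telephone visit from the in-clinic visits at Weeks 4, 8 and 12.

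Four other SAP rules bear on the same participant:

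- **SAP 6** leaves people out of the Safety Population if they returned all their drug, or if no follow-up indicates that they took any.
- **SAP 10.1** counts new-onset events as treatment-emergent "through ten days after the last dose of study medication".
- **SAP 7.3.1** separates pre-treatment from treatment-emergent events by a CRF question on whether the event began before the first dose. It has no upper time limit.
- **SAP 11.1** ends the concomitant-medication window ten days after the last dose.

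**The concern.** The imputation works when the last clinic visit comes after some period of treatment. It breaks down when that visit is Visit 2 itself, because the day before Visit 2 is before any drug was taken. The SAP then accepts a participant as treated, on the strength of the call, and records no days of treatment.

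The tablet-based measure does not fill the gap. Under SAP 11.2, a period for which no bottles or tablets come back adds nothing to exposure days unless they are returned at a later visit.

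The exposure summary is directly at stake. The treatment-emergent classification of events reported at the call, and the concomitant classification of some medications, are at stake only if the imputed date is carried into the ten-day windows.

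**Working it through.** The documents state no figure for this case, so there is none to reproduce. The check is date arithmetic with the SAP's own formulas, in protocol day numbering. The SAP's relabelling of Day 0 as Day 1 does not matter, because the formulas use dates.

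**Inputs**

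- First dose: Day 0, evening (Protocol 9.2).
- Last attended clinic visit: Visit 2, Day 0 (the case considered).
- Call window: 14 - 3 = Day 11 to 14 + 3 = Day 17 (Protocol 10.3).
- Imputed last dose = last clinic visit - 1 (SAP 11.2).
- Duration = last dose - first dose + 1 (SAP 11.2).
- End of treatment-emergent window = last dose + 10 (SAP 10.1).

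**Exposure**

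- Imputed last dose = 0 - 1 = Day -1.
- Duration = -1 - 0 + 1 = 0 days. If the first dose was taken a day late, on Day 1, it is -1 - 1 + 1 = -1 day.

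**Treatment-emergent window, if it uses this date**

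- Window end = -1 + 10 = Day 9.

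| Call on | Days from window end to call | Onset days outside the window, up to the call | Duration if last dose were the evening before the call |
|---|---|---|---|
| Day 11 | 11 - 9 = 2 | 10 to 11 | 10 - 0 + 1 = 11 |
| Day 14 | 14 - 9 = 5 | 10 to 14 | 13 - 0 + 1 = 14 |
| Day 17 | 17 - 9 = 8 | 10 to 17 | 16 - 0 + 1 = 17 |

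Events with onset on Days 0 to 9 stay inside the window even when first reported at the call.

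**Contrast case.** If the last clinic visit is Visit 4 on Day 28, the last dose is Day 27, duration is 27 - 0 + 1 = 28 days, and the window ends on Day 37. The impossible date arises only when Visit 2 is the last clinic visit.

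**Scale, on an assumption.** The documents give no rate of loss between the call and Week 4. If it were 2% to 5% of 550, that would be 11 to 28 participants. The mean duration over 550 would then be understated by 11 × 11 / 550 = 0.2 days to 28 × 17 / 550 = 0.9 days. This range only shows scale and is not an estimate.

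**The case against.** The strongest reply is that this is an edge case in one exposure summary and that the safety consequences are not established. Much of that stands.

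- **Few people qualify.** The rule applies only to those lost to follow-up or with a missing last dose date. Protocol 10.5.1 asks withdrawing patients to attend an early-termination visit, and Protocol 10.5.2 allows unscheduled visits. Either would supply a later clinic date. A reader might infer that everyone whose last scheduled contact was the call is affected, but the documents do not support that.
- **The link to the ten-day windows is inferred.** The imputation sentence sits under exposure and compliance, and neither SAP 10.1 nor 11.1 refers to it. The reference to analysis purposes and the absence of any other last-dose rule make the link plausible, but it is not stated.
- **A second rule gives the opposite answer.** Under SAP 7.3.1 a Day 12 event is treatment-emergent whatever the last dose date. A reader might conclude that the plan drops on-drug events from the safety analysis. It cannot be read that firmly: two rules conflict. In any case SAP 10.1 lists all adverse events, SAP 10.1.2 summarises serious events with no stated treatment-emergent restriction, and SAP 10.1.3 lists deaths.
- **Most medications are unaffected.** SAP 7.3.1 treats a medication with a start date and no stop date as concomitant, so one still ongoing at the call counts. Only medications with a recorded stop date after Day 9 could fall outside the SAP 11.1 window, and all medications are still listed.

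A reader might also suppose that tolerability problems cluster among these early losses. The documents do not show this. SAP 9.1.1 names adverse events and loss to follow-up as separate reasons for discontinuation.

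None of this removes the exposure error. The SAP 11.2 rule is explicit, has no lower limit, and yields a last dose before the first.

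**Conclusion.** The point holds as a minor defect in the exposure derivation. For a participant lost to follow-up (or with a missing last dose date) after a Week 2 call that indicated dosing, and with no later visit of any kind, SAP 11.2 gives a last dose on Day -1 and a duration of 0 days. About 11 to 17 days would be expected if dosing ran to the evening before an in-window call.

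The effect on adverse events is conditional. If the imputed date is used in SAP 10.1, new events starting from Day 10 up to the call are not treatment-emergent there but are under SAP 7.3.1, so the two rules must be reconciled. Medications with a recorded stop date after Day 9 are exposed to the same effect under SAP 11.1.

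The size in the trial is unknown because the number affected is not given. Durations of 0 and of 11 to 17 days should both fall in the lowest exposure category (up to 4 weeks), so that table is unlikely to change. Efficacy analyses are not touched. The conclusion assumes a first dose on the evening of Day 0 and a call within its window.

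**What to change.** Amend SAP 11.2 so that the imputed last dose date comes from the latest contact with evidence of dosing, including the Week 2 telephone call, and is never earlier than the first dose date. Use that date for treatment duration and exposure.

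Add a sentence to SAP 10.1 and 11.1 stating which last-dose date applies to the ten-day windows, and whether SAP 7.3.1 or 10.1 decides treatment-emergent status.

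For illustration, if the existing day-before convention were applied to a call on Day 11, 14 or 17, duration would be 11, 14 or 17 days. The SAP 10.1 window would end on Day 20, 23 or 26, after the call in each case.

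The cost is a few SAP sentences and a small change to the derivation. No new assessment is needed, because compliance is already asked about at the call. The downside is that for telephone contacts the date rests on verbal report. The documents do not say that the call records a last-dose date, so the SAP should name the convention used.
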